6.1.2 ADMINISTRATION AND/OR DOSING

The study intervention, i.e. video viewing, will last 5-6 minutes and will be administered once via Qualtrics online.

6.2 FIDELITY

6.2.1 INTERVENTIONIST TRAINING AND TRACKING

N/A

6.3 MEASURES TO MINIMIZE BIAS: RANDOMIZATION AND BLINDING

After completion of consent and the pre-intervention survey that includes demographics, Qualtrics will direct participants into two separate survey branches: males and females. Qualtrics will randomize participants 1:1 to a video within each branch. They will then proceed to the post-intervention measures. Study staff will not know participants' arm assignment.

6.4 STUDY INTERVENTION/EXPERIMENTAL MANIPULATION ADHERENCE

In order to create common conditions for participants to the extent possible, participants will be instructed to complete the study in one sitting, on a tablet or computer, in a quiet place where they can concentrate. After the intervention, they will be asked to rate how fully they were able to concentrate on the video while it played.

6.5 CONCOMITANT THERAPY

N/A

6.5.1 RESCUE THERAPY

N/A

7 STUDY INTERVENTION/EXPERIMENTAL MANIPULATION DISCONTINUATION AND PARTICIPANT DISCONTINUATION/WITHDRAWAL

7.1 DISCONTINUATION OF STUDY INTERVENTION/EXPERIMENTAL MANIPULATION

N/A

7.2 LOST TO FOLLOW-UP

A randomized participant will be considered lost to follow-up if they fail to complete outcome measures. Participants who provide consent, are randomized, receive the study intervention, and subsequently withdraw will be considered randomized and will be analyzed in the arm assigned, consistent with intent-to-treat principles. Participants who provide consent but are not randomized and do not receive the study intervention will be replaced.

7.3 PARTICIPANT DISCONTINUATION/WITHDRAWAL FROM THE STUDY

A participant will be considered lost to follow-up if they fail to complete the study after providing consent and study staff are unable to contact the participant after at least 3 attempts. Participants may withdraw from participation in the study at any time.

8 STUDY ASSESSMENTS AND PROCEDURES

8.1 ENDPOINT AND OTHER NON-SAFETY ASSESSMENTS

Screening and eligibility assessments: Study staff with UW Health electronic health record (Health Link) access will identify biopsy patients and verify eligibility criteria in Health Link within 21 days of biopsy. If the patient appears to be eligible, a member of the study team will contact the patient via phone and mail (and

MyChart, if available through CHI2) to recruit them for the study. Patients will be provided a link to the study on Qualtrics, where they can answer questions to verify their eligibility criteria and proceed to participation if eligible. Eligibility criteria verified at each screening stage is described in **sections 5.1 and 5.2**. Reasons for screening patients out will be documented at each step of the process. Age and sex of eligible patients will be retained for all eligible patients, including those who decline to participate, to assess any bias between respondents and non-respondents.

Study data: Data will be collected virtually. Mode of data collection will not have adverse effects on our ability to test our study hypotheses. All study measurements will be entered by the participant into Qualtrics.

Baseline demographic and clinical characteristics: We will collect age, sex assigned at birth, clinical history of their thyroid, ethnicity, race, highest educational level attained, anxiety, and level of thyroid cancer fear.

Primary and secondary outcomes:

Type	Name	Timing of Measure	Brief description
Primary	Treatment choice	Post-intervention	We will assess patients' hypothetical treatment choice after the intervention. We will ask: "If you were the patient in the video and had recently been diagnosed with thyroid cancer, which of the two treatment options would you choose, knowing what you know right now?" Answers will include: removal of the entire thyroid, removal of half of the thyroid.
Secondary	Decision confidence	Post-intervention	We will assess patients' confidence in their treatment choice after the intervention. We will ask: "How confident do you feel that you are choosing the best treatment option for you?" Answers will range from 1 (not at all confident) to 10 (completely confident).
N/A	Manipulation check	Post-intervention	We will assess patients' engagement with the video with 5 items. Questions will ask about concentration and the extent to which the patient could identify with various aspects of the video. Response options are on a 7-point Likert scale ranging from 'completely disagree' [1] to 'completely agree' [7].
Secondary	Anxiety – STAI Brief	Baseline and Post-intervention	This 6-question, quantitative instrument was designed to assess state anxiety. ⁴⁷ Response options are on a 4-point Likert scale ranging from 'not at all' [1] to 'very much' [4]. Scores are totaled with a potential range of 6 to 24. We chose the STAI-6 because of its predictive validity in assessing changes induced by hypothetical choice experiments in patients with cancer. ^{41,45}
Secondary	Thyroid Cancer Fear (adapted)	Baseline and Post-intervention	This 8-question quantitative instrument was originally designed to assess fear of breast cancer in patients undergoing cancer screening. ⁴⁸ Items are rated on a 5-point scale from strongly disagree [1] to strongly agree [5]. We will adapt the measure to assess participants' fear of thyroid cancer. The score ranges from 8 to 40. For the original scale, low fear was defined as a total score of 8 to 15, moderate fear as a score of 16 to 23, and high fear as a score of 24 to 40.
Secondary	Jefferson Scale of Patient's Perceptions of Physician	Post-intervention	This 5-question quantitative instrument assesses patient perceptions of physician empathy. ⁵² Minor adaptations in wording were made to fit the video scenario. Response options are on a 7-point Likert scale ranging from

	Empathy (adapted)		'strongly disagree' [1] to 'strongly agree' [7]. Items are summed, with a max score of 35, and higher values indicating a perception of more empathy.
Secondary	Trust in Physician Scale (adapted)	Post-intervention	This 5-question quantitative instrument assesses patient trust in a physician. ⁴⁹ Response options are on a 5-point Likert scale ranging from 'strongly disagree' [1] to 'strongly agree' [5]. Responses are summed and scores are on a scale of 5 to 25, with higher values indicating more trust.
Tertiary	Information recall (adapted)	Post-intervention	This 5-question quantitative instrument assesses participants' level of recall of information in the video intervention. Questions were modeled after Decision Quality Instruments designed by [name], and colleagues at the MGH Health Decision Sciences Center. ^{53,54} Because our questions are novel, our exploratory analysis will be determined based on distribution and variability of results. Potential analyses include assigning participants a score based on how many answers are correct out of 5 and dichotomizing into "low" knowledge versus "high" knowledge, and/or comparing mean and median scores for the five questions across the two treatment groups. ⁵⁴

8.2 SAFETY ASSESSMENTS

N/A

8.3 ADVERSE EVENTS AND SERIOUS ADVERSE EVENTS

The current study will pose minimal risk to the participants. Participants will be made aware of the risks and benefits which they may incur from participating and will have time to ask questions. Further, they will be told their participation is voluntary and may leave the study at any time at no harm to them. Although no problems or adverse events are expected, any study related adverse events will be documented and reported to the local IRB per institutional policy. The PI is responsible for ensuring the safety of the participants and their data. All data collected will be used for research purposes only and only the study team members will have access to their information. Data will be protected as described previously and any noncompliance will be reported immediately.

8.3.1 DEFINITION OF ADVERSE EVENTS

8.3.2 DEFINITION OF SERIOUS ADVERSE EVENTS

8.3.3 CLASSIFICATION OF AN ADVERSE EVENT

8.3.3.1 SEVERITY OF EVENT

8.3.3.2 RELATIONSHIP TO STUDY INTERVENTION/EXPERIMENTAL MANIPULATION

8.3.3.3 EXPECTEDNESS

8.3.4 TIME PERIOD AND FREQUENCY FOR EVENT ASSESSMENT AND FOLLOW-UP

8.3.5 ADVERSE EVENT REPORTING

8.3.6 SERIOUS ADVERSE EVENT REPORTING

8.3.7 REPORTING EVENTS TO PARTICIPANTS

8.3.8 EVENTS OF SPECIAL INTEREST

8.3.9 REPORTING OF PREGNANCY

8.4 UNANTICIPATED PROBLEMS

8.4.1 DEFINITION OF UNANTICIPATED PROBLEMS

This protocol uses the definition of Unanticipated Problems as defined by the Office for Human Research Protections (OHRP). OHRP considers unanticipated problems involving risks to participants or others to include, in general, any incident, experience, or outcome that meets all of the following criteria:

- Unexpected in terms of nature, severity, or frequency given (a) the research procedures that are described in the protocol-related documents, such as the Institutional Review Board (IRB)-approved research protocol and informed consent document; and (b) the characteristics of the participant population being studied;
- Related or possibly related to participation in the research (“possibly related” means there is a reasonable possibility that the incident, experience, or outcome may have been caused by the procedures involved in the research); and
- Suggests that the research places participants or others at a greater risk of harm (including physical, psychological, economic, or social harm) than was previously known or recognized.

8.4.2 UNANTICIPATED PROBLEMS REPORTING

The principal investigator will report unanticipated problems (UPs) to the reviewing Institutional Review Board (IRB). The UP report will include the following information:

- Protocol identifying information: protocol title and number, PI’s name, and the IRB project number
- A detailed description of the event, incident, experience, or outcome
- An explanation of the basis for determining that the event, incident, experience, or outcome represents an UP
- A description of any changes to the protocol or other corrective actions that have been taken or are proposed in response to the UP

To satisfy the requirement for prompt reporting, UPs will be reported using the following timeline:

- Any UP will be reported to the IRB and to the funding agency within 14 business days of the investigator becoming aware of the problem
- All UPs should be reported to appropriate institutional officials (as required by an institution’s written reporting procedures), the supporting agency head (or designee), and the Office for Human Research Protections (OHRP) within 14 business days of the IRB’s receipt of the report of the problem from the investigator

8.4.3 REPORTING UNANTICIPATED PROBLEMS TO PARTICIPANTS

N/A

9 STATISTICAL CONSIDERATIONS

9.1 STATISTICAL HYPOTHESES

Primary Endpoint: We hypothesize that emotionally supportive communication will decrease patient preference for total thyroidectomy immediately after watching the video.

Secondary Endpoints: We hypothesize that emotionally supportive communication will decrease anxiety and thyroid cancer fear and increase trust, perceived empathy, and decisional confidence immediately after watching the video.

Tertiary/exploratory: We hypothesize that emotionally supportive communication will increase information recall immediately after watching the video.

9.2 SAMPLE SIZE DETERMINATION

We assume based on existing data that the proportion of participants choosing total thyroidectomy will be 0.89 and estimate the sample size needed for 90% power to detect a proportion lower than 89%. With a sample of n=59 in each group, we will be able to detect risk differences of -25% and medium effect sizes of -0.60 with 90% power using a 2-sided test (chi square for binary outcome) with Type I error rate alpha= 0.05. The UW Thyroid Nodule Biopsy clinic performs over 500 biopsies annually, of which approximately 70% are benign. The UW Radiology clinic performs 400 biopsies per year on patients with benign thyroid nodules.

We anticipate missing data will be very low as the study is expected to be completed in one sitting.

9.3 POPULATIONS FOR ANALYSES

We will perform a two-group intent to treat analysis based on the intervention randomization.

9.4 STATISTICAL ANALYSES

9.4.1 GENERAL APPROACH

For descriptive statistics, categorical and continuous data will be presented as percentages, means with standard deviations, median, and range. For inferential tests, we will use 2-sided tests with Type I error rate alpha=0.05 for statistical significance. Covariates are specified below. Checks for assumptions of normality will be performed. If data are not normal, nonparametric tests will be used.

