9.4.3 ANALYSIS OF THE SECONDARY ENDPOINT(S)

We will calculate distributional characteristics and perform a two-group intent to treat analysis for continuous or ordinal endpoints using 2-sided t-tests or analysis of variance (ANOVA) with Type I error rate alpha= 0.05, and risk differences or mean differences with confidence intervals for quantification and estimation of effect.

Secondary endpoint	Dependent on primary endpoint?	Repeated measure?	Scale	Statistical procedures
Decision confidence	No	No	Continuous	2-sided t-tests
Anxiety – STAI Brief	No	Yes: Pre and Post	Continuous	2-sided t-tests
Thyroid Cancer Fear	No	Yes: Pre and Post	Continuous and Ordinal	2-sided t-tests and ANOVA
Patient Perception of Physician Empathy	No	No	Continuous	2-sided t-tests
Trust in Physician	No	No	Continuous	2-sided t-tests
Information recall	No	No	Continuous	2-sided t-tests

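### Sections 9.4.1 and 9.4.3 leave the secondary scores to unadjusted t-tests that an undefined normality check can override; one prespecified adjusted mean-based model per score would be better

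*Combined protocol and SAP*

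**What the plan says.** Section 9.4.1 calls for a check of normality and then sets the general rule: "If data are not normal, nonparametric tests will be used". It does not name the check, its threshold, the quantity checked (raw score, change or residual), the replacement test, or the estimate to report with that test. It also says that covariates follow later in the plan.

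Section 9.4.3 lists two-sided t-tests for every score, with ANOVA added for fear, and promises "risk differences or mean differences with confidence intervals for quantification and estimation of effect". No covariate is named for any of these scores. Anxiety and fear are marked as measured before and after the video, but the section does not say whether the t-test compares post-video scores or changes. Sex, the randomisation stratum in section 6.3, enters only the primary analysis (section 9.4.2).

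Section 9.2 sizes the trial: "With a sample of n=59 in each group, we will be able to detect risk differences of -25% and medium effect sizes of -0.60", at 90% power and a two-sided 5% level.

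Section 8.1 describes the scores, all of them bounded and discrete: confidence 1-10, STAI-6 6-24, fear 8-40, empathy up to 35, trust 5-25, and recall out of 5. Recall is tertiary, and section 8.1 openly leaves its analysis to depend on the observed distribution.

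**The concern.** The plan names one analysis and then lets an unspecified look at the outcome data replace it, endpoint by endpoint. Two analysts following the text could reach different tests for the same score, and either could be defended after the data are seen. Where the switch happens, the p-value comes from a rank comparison while the effect estimate in section 9.4.3 is a mean difference. The two can disagree, and nothing says which governs.

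Separately, the planned t-tests make no use of the sex stratum, or of the baseline anxiety and fear scores as covariates, although all are collected before the video. Both gaps can be closed by the same edit, so they are taken together here, but their consequences differ and are kept apart below.

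**Working it through.** **1. The plan's own figure.** Inputs from section 9.2: proportions 0.89 and 0.64 (0.89 - 0.25), standardised effect 0.60, two-sided 5%, power 90%.

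- Means: n = 2(1.960 + 1.282)² / 0.60² = 2 × 10.51 / 0.36 = 58.4, so 59 per group. Power at 59 is 0.903 (0.898 by noncentral t).
- Proportions, uncorrected chi-square: n = [1.960 × √(2 × 0.765 × 0.235) + 1.282 × √(0.89 × 0.11 + 0.64 × 0.36)]² / 0.25² = (1.175 + 0.734)² / 0.0625 = 58.3, so 59. Power at 59 is 0.903.

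The stated size reproduces and is not in question.

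**2. How often the switch would fire.** The documents give no distributions and no named check, so both are assumed. Scores were simulated as sums of discrete items on the planned ranges, with latent inter-item correlation 0.5 and 59 per arm, from symmetric to strongly skewed, 2,000 trials per scenario. The trigger was Shapiro-Wilk p < 0.05 on pooled residuals.

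| Score | Symmetric | Mild skew | Moderate skew | Strong skew |
|---|---|---|---|---|
| Confidence (single item) | 92% | 100% | 100% | 100% |
| STAI-6 | 11% | 17% | 69% | 100% |
| Fear | 6% | 18% | 88% | 100% |
| Empathy | 9% | 40% | 99% | 100% |
| Trust | 9% | 25% | 95% | 100% |

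Recall (0-5 correct) fired in about 100% of trials whether 50% or 90% of answers were correct. The definition of the check matters too: testing each arm separately moves symmetric STAI-6 from 11% to 21%.

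**3. What the switch does to validity and power.** In the same runs (Monte Carlo standard error about 0.005) type I error was:

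- t-test 0.045-0.056, including 0.048 at skewness -1.28 with half the answers at the ceiling;
- Wilcoxon 0.043-0.056;
- the two-stage rule 0.044-0.056.

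Power of the t-test and Wilcoxon differed by no more than about 0.02; further runs put the gap at no more than about 0.04.

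**4. What baseline adjustment does.** With pre-post correlation ρ (not given; assumed 0.3 to 0.7), adjustment multiplies the residual SD by √(1 - ρ²). Power = Φ(d√(59/2) / √(1 - ρ²) - 1.960). At d = 0.40, d√(59/2) = 2.173.

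- Unadjusted: Φ(2.173 - 1.960) = 0.58.
- ρ = 0.3: Φ(2.173/0.954 - 1.960) = 0.63 (0.625 unrounded to two places).
- ρ = 0.5: Φ(2.173/0.866 - 1.960) = 0.71.
- ρ = 0.7: Φ(2.173/0.714 - 1.960) = 0.86.

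At d = 0.60, power goes from 0.903 to 0.927, 0.964 and 0.995.

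If the planned t-test is on changes instead, its SD factor (equal variances) is √(2(1 - ρ)) = 1.183, 1.000 and 0.775. Power at d = 0.40 is then 0.45, 0.58 and 0.80, still below the adjusted figures.

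**5. Both together.** A skewed STAI-like score with latent correlation 0.7 was simulated 1,500 times:

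| Analysis | Type I error | Power, latent shift 0.6 |
|---|---|---|
| t-test | 0.045 | 0.806 |
| Wilcoxon | 0.043 | 0.790 |
| Linear model with baseline and sex | 0.052 | 0.927 |
| Rank version with baseline and sex | 0.049 | 0.913 |

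The step from t-test to Wilcoxon costs 0.016; the step from t-test to the adjusted model gains 0.121. These runs used ordinary standard errors and gave sex no effect on the score, so they show nothing about the size of any gain from sex.

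**The case against.** A reader might infer several stronger things, and the documents do not support them.

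- **That the switch will fire for almost every secondary scale.** This is near certain only for confidence. For the sum scales it depends on skew that the documents do not give and on a check that they do not name. Recall is tertiary.
- **That the switch blocks baseline and sex adjustment.** Section 9.4.3 plans none, so there is nothing to block. Only two of the five secondary scores have a baseline, and rank methods can be adjusted or stratified, as the last row above shows.
- **That the switch causes a loss of power.** Comparing a rank test with a baseline-adjusted model measures the missing adjustment. Against the planned t-test, the rank test has nearly the same power.
- **That the planned mean differences are dropped, or that sections 9.2 and 9.4.3 are contradicted.** Section 9.4.1 changes tests; nothing withdraws the estimates, and a fallback beside a default test is not a contradiction.

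It can fairly be added that no type I inflation was found and that the adjusted model goes beyond repairing one sentence. All of this stands, and it limits the point. It does not justify the sentence: if both tests are valid with similar power, the switch has no purpose, while the choice of test stays open and the p-value need not match the estimate. The adjusted model is worth adding on its own merits.

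**Conclusion.** The point holds as a prespecification gap joined to a missed improvement in the secondary analyses. The normality switch is undefined, gains no validity at 59 per arm, and can pair a rank p-value with a mean difference that it does not test. Its harm is loss of a fixed, interpretable analysis, not error inflation or lost power. The power gain comes from using the baseline score, and only for anxiety and fear: at d = 0.40, from about 0.58 to between 0.63 and 0.86.

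The firing rates rest on assumed score shapes and an assumed Shapiro-Wilk trigger, and the power gain on assumed correlations of 0.3 to 0.7. That the t-test keeps its size held in every shape tried. The primary endpoint and the sample size are untouched. The change should be made, but the trial's main conclusion does not depend on it.

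**What to change.** Remove the switch sentence from section 9.4.1 and replace the t-test and ANOVA entries for the secondary scores in section 9.4.3 with one prespecified analysis:

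- a linear model for each post-video score with terms for arm and sex, plus the baseline score for STAI-6 and fear, used whatever the distribution;
- the mean difference between arms with its 95% confidence interval, from heteroscedasticity-robust standard errors of a named type;
- a sex-stratified rank test as a sensitivity analysis only.

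Naming these terms also supplies the covariates that section 9.4.1 promises. Recall can stay labelled exploratory, with the table in section 9.4.3 brought into line with section 8.1.

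The cost is plan wording, settled before outcomes are analysed by arm. No new data or participants are needed. The downside is small: a mean difference on a strongly skewed score is a partial summary, so the rank result should be shown beside it.

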9.4.2 ANALYSIS OF THE PRIMARY ENDPOINT(S)

The primary endpoint, treatment choice, is a binary scale. It will be measured once immediately after the intervention.

We will calculate distributional characteristics and perform a two-group intent to treat analysis for this binary endpoint using conditional logistic regression to account for stratification by sex. The Type I error rate alpha= 0.05.

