3 OBJECTIVES AND ENDPOINTS

OBJECTIVES	ENDPOINTS	JUSTIFICATION FOR ENDPOINTS
Primary		
Test the extent to which increased emotionally supportive communication by surgeons is associated with patient preference for total thyroidectomy.	We will measure which treatment participants would choose if they were the patient with thyroid cancer in the video (total thyroidectomy or hemithyroidectomy) immediately after they finish watching the video.	Treatment choice is the primary endpoint because prior studies in different populations indicate increased emotional support can influence medical choices. Emotionally supportive communication is most likely to impact patient preference in the short-term, as the treatment decision is being made.
Secondary		
Test the extent to which increased emotionally supportive communication by surgeons is associated with anxiety, thyroid cancer fear, perceived empathy, trust, and decisional confidence.	We will measure these endpoints immediately after participants finish watching the video, using the State Trait Anxiety Inventory brief, an adapted Cancer Fear Scale an adapted Trust in Physician Scale, an adapted Jefferson Scale of Patient's Perceptions of Physician's Empathy, and decisional confidence using a single-item 10-point Likert scale.	These secondary endpoints were selected because they represent potential emotion-related outcomes in the treatment decision-making process. Prior studies indicate the increased emotionally supportive communication can influence these outcomes in other medical settings.
Tertiary/Exploratory		
Test the extent to which increased emotionally supportive communication by surgeons is associated with information recall.	We will assess information recall immediately after participants finish watching the video with 5 multiple choice questions that ask about information relayed in both intervention videos.	Published data suggest that heightened emotional states can inhibit information processing and recall. Response to this heightened state with increased emotional support may improve recall.

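### Does the primary analysis of treatment choice need a prespecified risk difference with a confidence interval?

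*Combined protocol and SAP*

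**What the plan says.** The primary objective in Section 3 is worded "Test the extent to which increased emotionally supportive communication by surgeons is associated with patient preference for total thyroidectomy". Section 9.2 assumes that "the proportion of participants choosing total thyroidectomy will be 0.89" and states that with 59 per arm "we will be able to detect risk differences of -25% and medium effect sizes of -0.60 with 90% power using a 2-sided test"; the sizing test is a chi-square at alpha 0.05.

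Section 9.4.2 is the whole primary analysis. It says the distribution of the endpoint will be described, and it plans a "two-group intent to treat analysis for this binary endpoint using conditional logistic regression to account for stratification by sex" at alpha 0.05. It mentions no odds ratio, risk difference or interval. Section 9.4.1 adds that "categorical and continuous data will be presented as percentages, means with standard deviations, median, and range".

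An interval is mentioned only in Section 9.4.3, which plans "risk differences or mean differences with confidence intervals for quantification and estimation of effect". That sentence sits under the secondary endpoints and concerns continuous or ordinal measures. Every row of the table beneath it is labelled continuous, or continuous and ordinal. The one secondary or exploratory measure that could become binary is information recall, for which Section 8.1 lists "assigning participants a score based on how many answers are correct out of 5 and dichotomizing into" low and high knowledge among several possible analyses.

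**The concern.** The trial is described on one scale and analysed on another. Conditional logistic regression eliminates the sex-specific intercepts, so it returns a single coefficient and no fitted risk for either arm; a risk difference cannot be read off the model. The outcome is expected to be very common in the control arm, and there an odds ratio looks far larger than the change in the proportion. At the design values it is a 78% cut in odds for a 28% relative fall in the proportion choosing total thyroidectomy. The odds ratio also does not fix the absolute effect unless the control rate is known, and 0.89 is an assumption that analogue patients may not meet.

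Read literally, the plan promises estimates with intervals for secondary endpoints and none for the primary one. If the odds ratio were published alone, a reader could not set the result against the 25 points used in planning.

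**Working it through.** **Inputs.** Section 9.2: control proportion 0.89; difference -0.25, so 0.64 in the supportive arm; 59 per arm; two-sided alpha 0.05; power 90%. Section 6.3: 1:1 allocation within sex. The documents give neither the share of men nor the effect of sex on choice, so figures below that need them rest on stated assumptions.

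**1. The plan's own figure.** Pooled-variance chi-square without continuity correction, mean proportion (0.89 + 0.64)/2 = 0.765:

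n = [1.960 × √(2 × 0.765 × 0.235) + 1.2816 × √(0.89 × 0.11 + 0.64 × 0.36)]² / 0.25²
= [1.175 + 0.734]² / 0.0625 = 58.3, rounded up to 59 per arm.

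Power at 59 per arm is 0.903. The sizing reproduces.

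**2. The design point on three scales.**

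- Risk difference: 0.64 - 0.89 = -0.25. SE = √(0.89 × 0.11/59 + 0.64 × 0.36/59) = 0.0746. Half-width 1.96 × 0.0746 = 14.6 points, so -40 to -10 points.
- Odds ratio: (0.64/0.36)/(0.89/0.11) = 0.22, 95% CI 0.08 to 0.58 (unstratified approximation).
- Risk ratio: 0.64/0.89 = 0.72, 95% CI 0.58 to 0.89.

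All three come from the same two proportions and arm sizes, which the plan already commits to summarising.

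**3. Does the odds ratio alone mislead?** Holding it at 0.22, the risk difference is -14 points at a control rate of 0.95, -25 at 0.89, -33 at 0.80 and -36 at 0.70 (rates other than 0.89 are illustrative). So it would, if it stood alone. Beside the arm percentages the ambiguity disappears, because the control rate is then on the page.

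**4. Does ignoring the sex strata distort the difference a reader would compute?** Assume 12 men and 47 women per arm, with total thyroidectomy chosen by 10/12 men and 43/47 women in the control arm, and by 7/12 and 31/47 in the supportive arm.

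- Conditional logistic regression: one parameter, odds ratio 0.21 (0.08 to 0.56), p = 0.002.
- Crude difference: 38/59 - 53/59 = -15/59 = -25.4 points. SE = √(0.644 × 0.356/59 + 0.898 × 0.102/59) = 0.0737, so -39.9 to -11.0.
- Mantel-Haenszel difference: weights 12 × 12/24 = 6 for men and 47 × 47/94 = 23.5 for women. (6 × (-3/12) + 23.5 × (-12/47))/29.5 = (-1.5 - 6.0)/29.5 = -25.4 points, with interval -39.8 to -11.0.

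When the arms are equal within each sex, the two estimates are identical by construction. Under simple randomisation within sex (assumed 20% male, sex effect of 0 to 20 points), adjustment moves the estimate by 0.4 to 1.2 points on average. That is 0.4/14.6 = 3% to 1.2/14.6 = 8% of the half-width. Simulated coverage (assumed 10 to 30% male, 0- to 20-point sex effect) is about 0.94 to 0.95 for both intervals, and their half-widths differ by about 0.1 to 0.6 points.

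**5. Would adding an interval be free?** Nearly. In simulation with equal arms within sex (assumed 10 to 30% male, 0- or 10-point sex effect), the Mantel-Haenszel interval and the score test of the conditional model disagree about significance in 0.9 to 1.2% of trials at 0.89 against 0.64, and in about 3% at 0.89 against 0.74. A prespecified interval would therefore need a note that the p-value stays with the planned model.

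**The case for a change.** The best argument for a change is that the primary objective asks about extent, that Section 9.4.2 names no estimator, and that this leaves the choice among odds ratio, risk ratio, and crude or adjusted risk difference open until the data are seen. A few sentences would close it at no cost in patients or alpha. Section 9.4.3 does not rescue the plan, since on its face it covers other endpoints.

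Part of this stands. The text is silent on the effect measure, the planned model cannot supply a risk difference, and the documents do not settle what the phrase in Section 9.4.3 was meant to cover. Treatment choice is the only endpoint the plan defines as binary, so the phrase may have been intended for it and misplaced; a dichotomised recall score is the other reading.

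The rest carries little weight. The candidate measures summarise the same proportions and share the same null, and the test that decides the trial is fixed, so choosing among them cannot turn a negative result into a positive one. The mismatch of scales is also weaker than it looks: the alternative in Section 9.2 is a pair of proportions, and it is as much an odds ratio of 0.22 as a difference of 25 points. The objective's wording names no effect measure, and the secondary and exploratory objectives use the same form. Insisting on Mantel-Haenszel over a crude or standardised difference would be a preference, given how little they differ here.

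**Conclusion.** No change to the plan is needed. Section 9.4.2 omits an effect measure and interval, but following it as written produces no bias, no loss of power or precision, and no different conclusion. The arm percentages are already promised. The risk difference and its interval follow from them in one line, and any competent report of a two-arm binary endpoint would include them. At the design values that is -25 points (-40 to -10). Taking sex into account changes it by about a point at most on average.

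This rests on three assumptions: that the arm percentages and numbers are published beside the odds ratio, as Sections 9.4.1 and 9.4.2 imply; that missing outcomes are few, as Section 9.2 expects; and that the share of men and the effect of sex lie within the ranges shown. The scope of the risk-difference phrase in Section 9.4.3 is a point of drafting on which no result depends.
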